2.3 RISK/BENEFIT ASSESSMENT

2.3.1 KNOWN POTENTIAL RISKS

Overall, this research study poses no more than minimal risks to participants. The single-arm pilot study of BRIGHT and single-site pilot RCT comparing BRIGHT with AC were minimal risk studies that were approved by the Medical University of South Carolina (MUSC) Institutional Review Board (IRB) under an expedited review (45CFR46.110). The proposed study will use a single IRB structure with MUSC serving as the IRB of record. No formal Data and Safety Monitoring Board was required in the prior studies of BRIGHT, although a Data and Safety Monitoring Plan (DSMP) with principal investigator (PI) and IRB-based oversight was created. The main study procedures include (1) either BRIGHT (CBT) or AC (a manualized tele-supportive care intervention that controls for professional attention, dose, delivery method, and common factors) and (2) completion of study questionnaires. These are generally considered minimal risk activities, although one of the questionnaires inquires about suicidal ideation. There are no physical, financial, legal, social, or cultural, risks to the study participants by joining this study. The primary risks of the study associated with the intervention or study assessments include psychological/emotional distress and breach of privacy/confidentiality.

Psychological/emotional distress: Subjects may experience adverse psychological reactions such as anxiety, depression, stress, distress, or suicidal ideation as a result of discussing issues related to cancer, body image, stigmatization, isolation, coping strategies, or social support. These issues may occur during the completion of study questionnaires (baseline or post-treatment) or during the intervention (BRIGHT or AC). However, based on our experience with prior similar trials, we expect only minimal risk to participants. Nevertheless, we have a specific protocol to address situations in which a patient becomes distressed as a result of either the study intervention or study assessments. The project coordinator and all of the study interventionists have extensive experience dealing with this patient population and appropriate safeguards have been put in place to mitigate against this risk in either situation. There is a licensed clinical psychologist at each site that is trained in assessing and intervening upon distress.

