8.4 ADVERSE EVENTS AND SERIOUS ADVERSE EVENTS

8.4.1 DEFINITION OF ADVERSE EVENTS

This trial is considered to carry a low risk to subjects (i.e. has a "no more than minimal risk" designation). As such, this protocol defines an adverse event (AE) as any sustained undesirable psychological, social, or emotional reaction that is definitely, probably, or possibly related to the study intervention. AEs include suicide attempt, sustained emotional distress, sustained depression, or other sustained mental health deterioration. This definition of an adverse event follows best practices for recording adverse events during psychological treatments.⁹⁹

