8.4.2 DEFINITION OF SERIOUS ADVERSE EVENTS

A serious adverse event (SAE) will be defined as any sustained undesirable psychological or mental health condition which is fatal, is life-threatening, requires or prolongs inpatient hospitalization, results in persistent or significant disability/incapacity, is medically significant and which the investigator regards as serious based on appropriate medical judgment that is directly due to a study intervention. An important medical event is any AE that may not result in death, be life-threatening, or require hospitalization but may be considered an SAE when, based upon appropriate medical judgment, it may jeopardize the patient and may require medical or surgical intervention to prevent one of the outcomes listed in the definitions of SAEs.

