8.4.3.2 RELATIONSHIP TO STUDY INTERVENTION/EXPERIMENTAL MANIPULATION

All AEs will have their relationship to study procedures, including the intervention, assessed by the PI based on temporal relationship and his clinical judgment. The degree of certainty about causality will be graded using the categories below.

- **Definitely Related** – There is clear evidence to suggest a causal relationship, and other possible contributing factors can be ruled out. The clinical event, including an abnormal laboratory test result, occurs in a plausible time relationship to study procedures administration and cannot be explained by concurrent disease or other drugs or chemicals. The response to withdrawal of the study procedures should be clinically plausible. The event must be pharmacologically or phenomenologically definitive.
- **Probably Related** – There is evidence to suggest a causal relationship, and the influence of other factors is unlikely. The clinical event, including an abnormal laboratory test result, occurs within a reasonable time after administration of the study procedures, is unlikely to be attributed to concurrent disease or other drugs or chemicals, and follows a clinically reasonable response on withdrawal.
- **Possibly Related** – There is some evidence to suggest a causal relationship (e.g., the event occurred within a reasonable time after administration of study procedures). However, other factors may have contributed to the event (e.g., the participant's clinical condition, other concomitant events). Although an AE may rate only as "possibly related" soon after discovery, it can be flagged as requiring more information and later be upgraded to "probably related" or "definitely related", as appropriate.

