
9.4.4 SAFETY ANALYSES

All patients in the SAS will be evaluated for safety and toxicity. Adverse events, SAEs and will be summarized. Safety analyses will include the following summaries:

- AEs, including severity and relationship to a study intervention
- SAEs, including relationship to a study intervention

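### Section 8.4.2 sets a stricter, undefined causality condition for serious adverse events than 8.4.1 and 8.4.3.2 use for adverse events, so a grave event judged only possibly related can miss SAE classification and reporting.

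*Protocol*

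**What the plan says.** Protocol 8.4.1 defines an AE as a sustained, undesirable psychological, social or emotional "reaction that is definitely, probably, or possibly related to the study intervention". Suicide attempt is a listed example.

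Protocol 8.4.2 has two sentences. The first lists the seriousness criteria (death, threat to life, hospitalisation, disability, medical significance in the investigator's judgement) and ends with "that is directly due to a study intervention". The second adds a category and opens with "An important medical event is any AE that may not result in death, be life-threatening, or require hospitalization". Under it, such an event can be classed as an SAE on medical judgement if the patient is put at risk. It does not repeat the causality clause.

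Protocol 8.4.3.2 says "All AEs will have their relationship to study procedures, including the intervention, assessed by the PI" and gives three grades: definitely, probably and possibly related. A possible rating may later be upgraded.

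Protocol 8.4.5 has all AEs collected and reported. Protocol 8.4.5 and 8.4.6 send the evaluation of each SAE to NIH and the reviewing IRB as soon as possible. Protocol 9.4.4 plans to summarise "SAEs, including relationship to a study intervention".

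**The concern.** Seriousness and causality are separate questions, and the first sentence of 8.4.2 merges them. Its condition is tighter than the one that makes an event an AE, and it uses a term that the protocol's causality scale does not contain. A grave event can therefore satisfy the AE definition and a seriousness criterion and still not be an SAE.

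The possible grade is likely to arise in this trial. Section 8.4.3.2 assigns it where other factors, such as the participant's clinical condition, may have contributed. Participants are recent cancer survivors selected for distress, and Sections 2.1 and 2.2.2 stress raised suicide mortality in head and neck cancer survivors.

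Prompt reporting outside the study team depends on the SAE label. Safety oversight is by the PI through monthly aggregate review (9.5.7), and clinical monitoring is marked not applicable (9.5.8).

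**Working it through.** No arithmetic applies. The check compares the definitions and follows example events through them.

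**Step 1: thresholds side by side**

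| Place | Causality condition |
|---|---|
| 8.4.1, AE | "definitely, probably, or possibly related to the study intervention" |
| 8.4.2, first sentence, SAE | "that is directly due to a study intervention" |
| 8.4.2, second sentence, important medical event | any AE, so at least possibly related |
| 8.4.3.2, grading scale | definitely, probably or possibly related |
| 9.4.4, SAE summary | by relationship, which presupposes that relationship varies among SAEs |

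The condition in the second row appears nowhere on the scale in the fourth.

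**Step 2: two ways to read the first sentence of 8.4.2**

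Reading A, the plain one: the closing clause governs every criterion in the list. Reading B: it governs only the last, judgement-based criterion.

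| Event | AE under 8.4.1? | SAE, reading A | SAE, reading B |
|---|---|---|---|
| Suicide attempt with hospitalisation, possibly related | Yes | Not under the first sentence | Yes |
| Same event, probably related | Yes | Cannot be determined, because the term is undefined | Yes |
| Same event, definitely related | Yes | Yes, if a definite relation counts as direct | Yes |
| Not fatal, life-threatening or hospitalised, but judged to jeopardise the patient; possibly related | Yes | May be, through the second sentence | May be, through the second sentence |

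**Step 3: what follows**

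- Reading A inverts the order of gravity. The fourth event has a route to SAE status with no direct-causation test, while the first, graver event must pass that test.
- Reading B removes the inversion but leaves two problems. Medically significant events are covered by both sentences, once with the clause and once without. The remaining criteria carry no causality condition, so an unrelated hospitalising mental health condition would be an SAE without being an AE.
- The summary in 9.4.4 has its natural meaning only if SAEs can carry different grades. A definition that already requires direct causation fits poorly with that.

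**Step 4: intervention or procedures**

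Section 8.4.1 refers only to the intervention, whereas 8.4.3.2 grades relation to study procedures, including the intervention. Section 2.3.1 expects that distress may arise while questionnaires are completed, including at baseline. Section 8.4.4 starts AE recording at consent, and 6.3 places the baseline assessments before randomisation. A reaction to the baseline questionnaires thus falls inside the recording period but outside the wording of 8.4.1.

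**The case against.** The strongest reply is that little is lost. Suicide attempt is named as an AE, all AEs are collected and reported (8.4.5), and 9.4.4 summarises them by severity and relationship. The PI reviews them monthly (9.5.7), and a possible rating can be upgraded (8.4.3.2). Possibly related events can also reach the IRB and NCI as unanticipated problems (8.5), and Section 2.3.3 has its own procedures for responding to suicidality. All of this stands, and it limits the consequence to the SAE label and its reporting.

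It does not remove the consequence. The unanticipated-problem route also requires that the event be unexpected and suggest greater risk than was known. Section 2.3.1 already lists suicidal ideation and distress as risks, so some grave events may not qualify.

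The second reply is reading B, on which a hospitalised suicide attempt is an SAE whatever its grade. The grammar allows this. But a sentence that gives opposite answers for the same event is itself a defect, because AE information is managed by separate teams at three sites.

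A reader might infer more than the text supports:

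- **That a possibly related event can never be an SAE.** The second sentence of 8.4.2 admits any AE on medical judgement.
- **That the probable and possible grades are both shut out, so that the 9.4.4 summary can hold only one category.** This equates direct causation with the definite grade, which the protocol does not do. A probably related event might be judged direct, and the second sentence lets other grades in.
- **That the comparison of safety between arms would be understated.** The AE summary keeps these events, and nothing in the protocol shows that the effect would differ by arm.

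**Conclusion.** The point holds as an inconsistency in the safety definitions that should be corrected. The causality condition in 8.4.2 is stricter than that in 8.4.1, undefined against 8.4.3.2, ambiguously placed, and in tension with both its own second sentence and 9.4.4. On the plain reading, a fatal, life-threatening or hospitalising event graded possibly related is an AE but lies outside the main SAE definition, and so outside the report required by 8.4.6.

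The effect is on classification and prompt reporting; the event stays in the AE data. Its size cannot be put as a number, because the protocol gives no expected event rates or distribution of grades. The conclusion rests on reading A. On reading B the risk to grave events largely disappears, but the ambiguity and the mismatches in Step 3 remain. The gap over study assessments is a related, secondary point and does not depend on which reading is taken.

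**What to change.** In 8.4.2, delete the clause "that is directly due to a study intervention". Define an SAE as any AE under 8.4.1 that meets a seriousness criterion, with its relatedness graded on the existing 8.4.3.2 scale. The important-medical-event sentence then agrees with the main definition, and the 9.4.4 summary can show all three grades. At least a possible relation is still required, because 8.4.1 builds it in.

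Also reconcile 8.4.1 with 8.4.3.2, 8.4.4 and 2.3.1 so that reactions to study assessments are covered, for example by referring in 8.4.1 to the study intervention or study procedures.

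The cost is an amendment to the protocol wording and the AE form. A few more events may be reported as SAEs. The design, sample size and efficacy analyses are unaffected.

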8.4.3 CLASSIFICATION OF AN ADVERSE EVENT

8.4.3.1 SEVERITY OF EVENT

- **Mild** – Events require minimal or no treatment and do not interfere with the participant's daily activities.

- **Moderate** – Events result in a low level of inconvenience or concern with the therapeutic measures. Moderate events may cause some interference with functioning.
- **Severe** – Events interrupt a participant's usual daily activity and may require systemic drug therapy or other treatment. Severe events are usually potentially life-threatening or incapacitating. Of note, the term "severe" does not necessarily equate to "serious".

8.4.3.2 RELATIONSHIP TO STUDY INTERVENTION/EXPERIMENTAL MANIPULATION

All AEs will have their relationship to study procedures, including the intervention, assessed by the PI based on temporal relationship and his clinical judgment. The degree of certainty about causality will be graded using the categories below.

- **Definitely Related** – There is clear evidence to suggest a causal relationship, and other possible contributing factors can be ruled out. The clinical event, including an abnormal laboratory test result, occurs in a plausible time relationship to study procedures administration and cannot be explained by concurrent disease or other drugs or chemicals. The response to withdrawal of the study procedures should be clinically plausible. The event must be pharmacologically or phenomenologically definitive.
- **Probably Related** – There is evidence to suggest a causal relationship, and the influence of other factors is unlikely. The clinical event, including an abnormal laboratory test result, occurs within a reasonable time after administration of the study procedures, is unlikely to be attributed to concurrent disease or other drugs or chemicals, and follows a clinically reasonable response on withdrawal.
- **Possibly Related** – There is some evidence to suggest a causal relationship (e.g., the event occurred within a reasonable time after administration of study procedures). However, other factors may have contributed to the event (e.g., the participant's clinical condition, other concomitant events). Although an AE may rate only as "possibly related" soon after discovery, it can be flagged as requiring more information and later be upgraded to "probably related" or "definitely related", as appropriate.

8.4.4 TIME PERIOD AND FREQUENCY FOR EVENT ASSESSMENT AND FOLLOW-UP

Recording/reporting of AEs will begin after the subject signs informed consent and end after the subject completes the intervention and follow up period as defined in the protocol. AEs may be reported by the patient via self-report, noted in the electronic medical record, or reported directly by study personnel.

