BRIGHT was effective at reducing HNC-related BID for the majority of patients. The waterfall plot demonstrating each patient's clinical response to BRIGHT or AC, as measured by change in IMAGE-HN scores from baseline to 3-months post-intervention, is shown in **Figure 5B**. At 3-months post-intervention, patients in BRIGHT had a 6.6-fold increase in the odds of clinical response (proportion of patients with a clinically meaningful decrease in IMAGE-HN scores of ≥ 9) relative to patients in AC (model-based odds ratio [OR] = 6.6 [90% CI, 2.0 to 21.8]; $p = 0.09$).⁷⁵

Mean Change from Baseline and Response of Head and Neck Cancer (HNC)-Related Body Image Distress for Patients in BRIGHT and Attention Control

[figure not shown]

Fig 5. A. Line graph demonstrating the mean change from baseline in IMAGE-HN scores over time by intervention allocation. Error bars represent 1 SE above and below the mean. **B.** Waterfall plot showing response to BRIGHT and Attention control, as measured by absolute change from baseline in IMAGE-HN scores at 3 months postintervention. IMAGE-HN scores range from 0 to 84, with higher scores indicating worse HNC-related BID (and negative bars thus indicating improvement in HNC-related BID). The dashed horizontal line at ± 9 indicates a clinically meaningful change in IMAGE-HN score.

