confidentiality is when there is the potential of danger of the participant to her/himself or to another person. For participants enrolled in the BRIGHT arm, the study interventions will be delivered by a licensed clinical psychologist at each site. Each psychologist is familiar with standard of care and best practices for the assessment and management of suicidal ideation during tele-CBT, which are described in detail in the BRIGHT Therapy Manual. During each BRIGHT session, the psychologist will establish the patient's physical location, nearest emergency medical service provider, and emergency contact information to ensure that the team can intervene if needed. A determination about the appropriateness of the participant for home-based tele-mental health care will be made including the adequacy of infrastructure and technology. Participants will be instructed of legal requirement break confidentiality to notify emergency services for a welfare check should there be concern for the participant or others safety and the participant cannot be properly evaluated by the clinical psychology team (e.g., lost contact with patient and patient cannot be reached again). During sessions, monitoring of risk will occur during treatment (symptom levels, self-harm ideation, intention to harm others, changes in setting/patient situation) as described in the DSMP. If suicidality is endorsed, staff will assess risk, including frequency, lethal means, intent, behavior, and plans. If risk is moderate to low (e.g., no intent or plan), the psychologist and patient will establish a safety plan, including identifying warning signs and internal coping strategies, having the patient or others remove lethal means (e.g., firearms, medication), activating social support, and accessing professional services. Each site will follow its own procedures for sharing regional, and/or national hotlines (e.g., National Suicide Prevention Lifeline = call or text 988). MUSC and Henry Ford also provide local call options (MUSC = [name], Henry Ford = [contact] at Henry Ford), while Washington University only uses national hotlines. If risk is deemed to be imminent, the psychologist will call emergency services for immediate psychiatric assessment.

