Similar procedures will be followed for the AC arm with modifications for the delivery of AC by the licensed clinical interventionist (e.g., nurse, advanced practice provider) instead of a psychologist. The clinical interventionist will receive standard training in best practices for the assessment and management of suicidal ideation during tele-medicine visits, which are described in detail in the SOP for AC. During each AC session, the clinical interventionist will establish the patient's physical location, nearest emergency medical service provider, and emergency contact information to ensure that the team can intervene if needed. A determination about the appropriateness of the participant for home-based tele-mental health care will be made including the adequacy of infrastructure and technology. Participants will be instructed of legal requirement break confidentiality to notify emergency services for a welfare check should there be concern for the participant or others safety and the participant cannot be properly evaluated by the clinical psychology team (e.g., lost contact with patient and patient cannot be reached again). During sessions, monitoring of risk will occur during treatment (symptom levels, self-harm ideation, intention to harm others, changes in setting/patient situation) as described in the DSMP. If suicidality is endorsed, the clinical interventionists will assess risk, including frequency, lethal means, intent, behavior, and plans. Then, the clinical interventionist will immediately engage the study psychologist at each site to assess risk. If that psychologist is not available, the clinical interventionist will contact the on-call psychologist at each site (who is available 24 hours a day). If risk is moderate to low (e.g., no intent or plan), the psychologist and patient will establish a safety plan, including identifying warning signs and internal coping strategies, having the patient or others remove lethal means (e.g., firearms, medication), activating social support, and accessing professional services. Local, regional, and/or national hotlines will be shared, as is done in standard practice at each site (e.g., National Suicide Prevention Lifeline = call or text 988). MUSC and Henry Ford also provide local call options (MUSC = [name], Henry Ford = [contact] at Henry Ford), while Washington University only uses national hotlines. If risk is deemed to be imminent, the licensed clinical interventionist will call emergency services for immediate psychiatric assessment.

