6 STUDY INTERVENTION(S) OR EXPERIMENTAL MANIPULATION(S)

6.1 STUDY INTERVENTION(S) OR EXPERIMENTAL MANIPULATION(S) ADMINISTRATION

6.1.1 STUDY INTERVENTION DESCRIPTION

6.1.1.1 BRIGHT

BRIGHT is a manualized theory-based tele-CBT intervention consisting of 6 weekly 60-minute sessions. BRIGHT will be delivered one-on-one by a licensed clinical psychologist at each site (MUSC, HFH, WUSM)

via standard video tele-CBT platform. BRIGHT is situated within a cognitive psychology perspective¹⁹ of BID and conceptualizes HNC-related BID according to Folkman's transactional theory of stress and coping.^{17,24,46,55} **Table 7** shows the psychotherapeutic techniques utilized in BRIGHT to address key theorized targets.

Psychologists deliver BRIGHT according to the BRIGHT Manual, which outlines the underlying theoretical basis of BRIGHT as well as the topics, objectives, psychotherapeutic techniques, and content for each session. Patients receive the BRIGHT Patient Workbook, which contains objectives, educational materials, exercises, and homework for each week. The BRIGHT materials were developed with engagement from HNC

Table 7. BRIGHT Psychotherapeutic Techniques and Objectives	
Technique	Session Objectives
Psycho-education	-Understand the cognitive model of body image and how HNC survivors are affected by BID
Self-Monitoring	-Learn how thoughts, feelings, and behaviors about body image are related -Begin to self-monitor situations that contribute to BID
Cognitive Restructuring	-Identify unhelpful automatic HNC body image schemas -Challenge unhelpful automatic HNC body image thoughts and substitute more balanced thoughts
Body Image Coping Strategies	-Identify body image avoidance behaviors and recognize how they increase long-term BID -Develop an action plan for situations that are being avoided
Relapse Prevention	-Reflect on progress made during BRIGHT -Set goals aligned with personal values to prevent relapse

survivors to ensure that the content was language and literacy-level appropriate and refined with HNC survivors from our single-arm trial and pilot RCT to optimize relevance, clarity, and readability.

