Psychologists at each site (MUSC, HFH, WUSM) have experience delivering video tele-mental health care to patients with HNC. The HIPAA-compliant and institutionally-approved video telemedicine platform at each site uses face to face communication and includes a within-video text feature for patients with challenges speaking due to surgical removal of the voice box or tongue. Although the COVID-19 pandemic rapidly accelerated the uptake of telemedicine for HNC survivorship care^{77,78} and CBT,^{79,80} the potential for a digital divide remains.⁸¹ To enhance equity and minimize the digital divide, we will provide patients with a study-issued, cellular-enabled iPad if needed, show patients how to use the iPad and telemedicine platform, and provide patients with a pictorial instructional booklet for home reference. Each iPad is locked to prevent downloading of additional applications, pre-loaded with a HIPAA-compliant video teleconference platform, and has cellular service with > 97% coverage for each state.⁸² Patients receive a pre-addressed, stamped, padded mailer to return the iPad. We successfully delivered BRIGHT using this approach in our single-arm trial¹⁶ and pilot RCT.

6.1.1.2 AC

Following best practices for choosing control groups within behavior change RCTs,^{83,84} we designed AC to control for professional attention (i.e., ensuring that findings are not driven by simply interacting with an empathic interventionist), common factors,²⁶ dose, and delivery method while not providing the active, behavior change mechanism in BRIGHT. AC is a manualized tele-supportive care intervention delivered by licensed HNC clinical staff (e.g., advanced practice provider) at each site (MUSC, HFH, WUSM) that addresses non-body image aspects of HNC survivorship. The AC manual provides educational content (**Table 8**) and directs the interventionist to provide empathic comments but contains no psychotherapeutic techniques. The manual also outlines the hypothesized behavior change mechanisms in BRIGHT that should not be addressed by AC and provides strategies for the interventionist to re-direct the conversation if BID arises. Identical to BRIGHT, AC consists of 6 weekly 60-minute sessions delivered by a trained empathic interventionist via standard video-telemedicine

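### Adverse events are collected without a structured tool and partly by staff who differ by arm, and Section 9.4.4 plans no count of worsening from the questionnaires both arms complete

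*Protocol*

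**What the plan says.** Protocol Section 8.4.1 defines an AE as "any sustained undesirable psychological, social, or emotional reaction that is definitely, probably, or possibly related to the study intervention". It sets no score threshold and names no instrument. Section 8.4.4 gives the routes of collection: "AEs may be reported by the patient via self-report, noted in the electronic medical record, or reported directly by study personnel". The Schedule of Activities (Section 1.3) has one AE row for both arms, marked at treatment sessions and at follow-up.

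The person who meets the patient each week differs by arm. Section 6.1.1.1: "BRIGHT will be delivered one-on-one by a licensed clinical psychologist at each site". Section 6.1.1.2: "AC is a manualized tele-supportive care intervention delivered by licensed HNC clinical staff". Section 2.3.3 draws the same contrast, describing for AC "modifications for the delivery of AC by the licensed clinical interventionist (e.g., nurse, advanced practice provider) instead of a psychologist". Section 6.1.1.2 also says that the AC manual gives staff ways to steer the conversation elsewhere when body-image distress comes up, and Section 6.2.2 has AC sessions checked to make sure that it is not discussed.

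The safety analysis in Section 9.4.4 consists of two listed summaries: "AEs, including severity and relationship to a study intervention", and the matching line for SAEs. Section 9.3 analyses the safety set by intervention received.

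On IMAGE-HN, Section 8.3.1 calls a change of 9 points or more clinically meaningful without naming a direction. The Fig 5 legend in Section 2.2.10 marks both directions: "The dashed horizontal line at ± 9 indicates a clinically meaningful change in IMAGE-HN score". The only responder endpoint (Table 5) counts decreases of at least 9.

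**The concern.** In this trial the harm of interest is psychological, and so is the skill needed to notice it. One arm meets weekly with a psychologist whose subject is body-image distress. The other meets weekly with clinic staff who are directed away from that subject. With no structured AE questionnaire, what study personnel report depends partly on who they are and what the session invites the patient to say.

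Two readings are then at risk. A higher AE count in BRIGHT could come from closer observation, and a low count in AC could mean that deterioration was not noticed. Better ascertainment cannot be recovered at the analysis stage. What can be added is a measure of worsening that does not pass through the interventionist. The protocol already collects such measures on one schedule in both arms, but Section 9.4.4 does not use them. A favourable mean change can coexist with a minority who clearly worsen, and no stated analysis counts that minority.

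**Working it through.** The protocol states no expected AE rate, detection rate or deterioration threshold for safety, so there is no figure to reproduce. The check is a comparison of sections, followed by an illustration on assumed values.

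**Routes of detection, side by side**

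| Route | BRIGHT | AC | Depends on arm? |
|---|---|---|---|
| Interventionist at weekly sessions (6.1.1.1, 6.1.1.2, 2.3.3) | Psychologist, body-image content | Clinic staff, body-image content redirected | Yes |
| Patient self-report (8.4.4) | Yes | Yes | Not by design |
| Medical record (8.4.4) | Yes | Yes | Not by design |
| AE check at follow-up (1.3) | Yes | Yes | Not by design |
| Beck scale flag in REDCap, checked daily, psychologist follow-up (2.3.3) | Yes | Yes | No |
| Listed in-session risk monitoring (2.3.3) | Yes | Yes; site psychologist engaged if suicidality is endorsed | Same list, different observer |

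One route clearly depends on arm and the others largely do not. The AC training described in Section 2.3.3 concerns suicidal ideation. The AE definition is wider: it also takes in sustained distress, depression and other mental health deterioration.

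**Illustration (all detection values assumed)**

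- Planned enrolment is 226 (Section 9.2), so 226 / 2 = 113 per arm.
- True risk is 10%, equal in both arms (assumed).
- s is the share of events caught by routes common to both arms (assumed 0, 0.5 or 0.8).
- Interventionist sensitivity is 0.9 in BRIGHT and 0.5 or 0.7 in AC (assumed).
- Detection = s + (1 − s) × sensitivity.
- Expected recorded AEs = 113 × 0.10 × detection.

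| s | Sensitivity, BRIGHT vs AC | Detection | Recorded AEs | Ratio |
|---|---|---|---|---|
| 0 | 0.9 vs 0.5 | 0.90 vs 0.50 | 10.2 vs 5.7 | 1.80 |
| 0 | 0.9 vs 0.7 | 0.90 vs 0.70 | 10.2 vs 7.9 | 1.29 |
| 0.5 | 0.9 vs 0.5 | 0.95 vs 0.75 | 10.7 vs 8.5 | 1.27 |
| 0.5 | 0.9 vs 0.7 | 0.95 vs 0.85 | 10.7 vs 9.6 | 1.12 |
| 0.8 | 0.9 vs 0.5 | 0.98 vs 0.90 | 11.1 vs 10.2 | 1.09 |
| 0.8 | 0.9 vs 0.7 | 0.98 vs 0.94 | 11.1 vs 10.6 | 1.04 |

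The true risk cancels from the ratio, so risks of 5% or 20% give the same ratios. The result depends mainly on how much the common routes catch, which the protocol does not tell us.

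**What the safety analysis leaves out.** Section 9.4.4 names AEs and SAEs only. IMAGE-HN, the PROMIS depression and anxiety forms and the Beck scale appear as efficacy changes (Sections 9.4.2 and 9.4.3). Section 8.3.1 states a Beck cutoff of more than 2, but nothing ties it to AE recording or to a safety summary.

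**The case against.** The strongest reply is that most detection routes are shared. Self-report, the record, follow-up checks and the Beck flag do not depend on who delivers the sessions. Section 2.3.3 lists the same in-session monitoring for both arms and offers the distress response to participants in either condition. Redirecting body-image talk does not forbid reporting an AE, and AC session 3 (Table 8) covers anxiety and depression. All of this stands. A reader might infer that AEs are found only by psychologists in one arm and only by clinic staff in the other, or that the AE table measures detection and not harm. The documents support neither reading.

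It is also fair that Section 9.4.4 names no between-arm test. Tabulation by arm is inferred from Section 9.3, though it is the natural reading in a two-arm trial. Nor are the questionnaires analysed for benefit only: they are modelled as continuous changes, so worsening enters the estimates, and the sample-size alpha is two-sided. Only the responder count runs in one direction. The subgroup analyses in Section 9.4.6 may show some heterogeneity, but they do not count individuals who worsen.

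Finally, a deterioration table could sit in the SAP, which is not shown. If it is already there, that part of the point is met. The collection method, however, is fixed in the protocol, and Section 9.4.4 sets out what the safety analyses will include.

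**Conclusion.** The point holds in a limited form. AE ascertainment is unstructured and partly arm-dependent, so a between-arm difference in AE counts may partly reflect detection. As written, Section 9.4.4 describes harm only through those events.

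The size cannot be estimated from the protocol. With equal true harm and the assumed values above, the spurious ratio runs from about 1.04 to 1.80. No single value in that range should be quoted as the expected bias. The direction shown, more events recorded in BRIGHT, follows from assuming that psychologists detect more; it is plausible but not demonstrated.

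The primary efficacy inference is unaffected. The stake is what the trial can say about worsening, in a study whose Section 2.3.1 names psychological or emotional distress among its primary risks.

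**What to change.** In Section 9.4.4, add one table by randomized arm, among all randomized patients with a baseline score and a score at the follow-up concerned:

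- the proportion with an IMAGE-HN increase of at least 9 points at 2, 3, 6 and 9 months, using the protocol's own clinically meaningful change;
- the proportion above the Beck cutoff of 2 stated in Section 8.3.1;
- the changes in PROMIS depression and anxiety.

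The last two are needed because IMAGE-HN measures body-image distress and does not cover everything in the AE definition. Give numerators and denominators, so that missing follow-up is visible. Add a sentence that AE and SAE counts are descriptive and that between-arm differences need cautious interpretation, because detection may differ by arm.

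The cost is one more table from data already collected, with no new assessment. The limit is that patients are not blinded (Section 6.3) and these scores are self-reported. The table removes the interventionist as detector but not every source of bias, and it does not change how AEs themselves are collected.
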